12.4 Analysis Datasets

12.4.1 Evaluable for Safety

This will be comprised of all subjects who receive at least one dose of trial drug.

12.4.2 Evaluable for Efficacy

Only those patients who have measurable disease present at baseline, have received at least one cycle of therapy, and have had their disease re-evaluated will be considered evaluable for response. These patients will have their response classified according to the definitions stated below. (NOTE: Patients who exhibit objective disease progression prior to the end of Cycle 1 will also be considered evaluable.)

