2 STUDY OBJECTIVES AND ENDPOINTS

2.1 Primary Objectives

2.1.1 Phase 1b

The primary objective of this study component is to determine the maximum tolerated dose (MTD) of PAC-1 in combination with entrectinib in patients with metastatic uveal melanoma, by evaluation of toxicity and tolerability.

2.1.2 Phase 2

The primary objective of this study component is to measure 3 months progression-free survival (PFS) rate in subjects with metastatic uveal melanoma treated with entrectinib and PAC-1.

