2.4 Primary Endpoints

2.4.1 Phase 1b

- The MTD of PAC-1 in combination with entrectinib is the highest tested dose of PAC-1 combined with entrectinib with DLT rate of less than 33% in first cycle of therapy (i.e., ≤ 1 out of 6 subjects with DLT).

2.4.2 Phase 2

- PFS at 3 months; this is defined as proportion of alive subjects with metastatic uveal melanoma at 3 months from treatment initiation with PAC-1 in combination with entrectinib without evidence of radiological disease progression by RECIST 1.1.

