4: A basic neurologic exam will be performed by the site investigator at screening, Day 1 of each Cycle of treatment and at the D30 safety follow up visit to monitor for neurologic toxicity. The Mini Mental Status Exam (MMSE) will be performed by a member of the research staff at screening and Day 1 of each Cycle of treatment to monitor for cognitive toxicity. The results of the MMSE and neurologic exam will be reviewed by the site investigator who will determine whether dose reduction of study drug(s) is required. This information should be retained.

5: CBC with differential and platelet to include: WBC, ANC, ALC, Hgb, PLT. Comprehensive metabolic profile (CMP) will be done at screening then Day 1 of each Cycle. During Cycle 1, a CMP should be performed at Cycle 1 Day 15. CMP to include glucose, calcium, BUN, creatinine, sodium, potassium, chloride, serum albumin, total bilirubin, alkaline phosphatase, AST, and ALT, ammonia, LDH and uric acid. Coagulation studies (PT/INR and PTT) will be done at screening then at the discretion of the treating investigator during treatment. For women of childbearing potential (WOCBP): urine or serum β hCG if clinically appropriate. If a urine test is done and it is positive or cannot be confirmed as negative, a serum pregnancy test will be required. Testing is required within 72 hours prior to initiation of study treatment. Urinalysis will be performed at screening.

6: Tumor response assessment will consist of evaluation by CT scans of chest and MRI or CT of abdomen and pelvis at screening and every odd numbered cycle starting after screening with CT scan before Cycle 3 (imaging selected for each subject should remain the same throughout the study); tumor imaging to be done at the safety follow up visit is at discretion of site investigator. If tumor assessments are available for subjects who have not yet experienced progressive disease (PD) at the time treatment is discontinued, the follow-up tumor evaluations will be documented in the eCRF until PD or death is confirmed, or until another treatment is initiated. MRI of the brain will be performed per standard of care for those subjects with a history of brain metastasis. A window of - 7 days may be used. CT/MRI images are to be submitted for central analysis. Images will be de-identified prior to sending to a central location. Central analysis to be performed upon receipt of funding.

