9.9.3 Progression-Free Survival

A measurement from the date of the start of treatment until the criteria for disease progression is met as defined by RECIST 1.1 or death occurs. Subjects who have not progressed will be right-censored at the date of the last disease evaluation.

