12.3.1 Number of subjects to be enrolled

Number to be enrolled:

Phase 1b: minimum of 9, maximum of 12

Phase 2: 6 subjects from MTD level in Phase 1b and an additional 29 subjects for a projected sample size of 35.

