12.5 Data Analysis Plans

12.5.1 Analysis Plans for Primary Endpoint

Phase Ib Analysis of Primary Endpoint

The primary endpoint is determination of the MTD of PAC-1 in combination with entrectinib. The MTD will be defined as the highest explored dose of PAC-1 combined with 600 mg of entrectinib at which ≤ 1 out of 6 subjects have experienced a DLT within the first cycle of therapy. That dose will be recommended for the Phase 2 study (i.e., will be declared the RP2D). At the discretion of the sponsor-investigator, a lower Phase 2 dose may be recommended if other toxicity emerges during the Phase Ib study which does not meet DLT criteria but limits the dose that can be administered cumulatively.

Phase II Analysis of Primary Endpoint

The primary endpoint is determination of the activity of the combination of PAC-1 and entrectinib for treatment of metastatic uveal melanoma, as assessed by 3 months PFS based on RECIST v1.1. Median PFS times will be computed with associated 95% confidence intervals. Kaplan-Meier curves will be plotted.

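### Section 12.5.1 assigns no population to Phase 2 3-month PFS, and the only efficacy set (12.4.2) leaves out deaths before the first scan, which the endpoint counts as failures

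*Combined protocol and SAP*

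**What the plan says.** - **Primary analysis (12.5.1).** Activity is to be judged "as assessed by 3 months PFS based on RECIST v1.1", with median PFS, 95% confidence intervals and Kaplan-Meier curves. No analysis set is named.
- **Analysis sets (12.4).** There are two. Section 12.4.1 takes everyone who received a dose and is labelled for safety. Section 12.4.2 is headed Evaluable for Efficacy, but its text concerns response: subjects must have measurable disease at baseline and "have received at least one cycle of therapy, and have had their disease re-evaluated will be considered evaluable for response". One exception follows: "Patients who exhibit objective disease progression prior to the end of Cycle 1 will also be considered evaluable". Death is not mentioned.
- **Endpoint (2.4.2).** The endpoint is the "proportion of alive subjects with metastatic uveal melanoma at 3 months from treatment initiation" who have no radiological progression.
- **PFS definition (9.9.3).** PFS runs from the start of treatment "until the criteria for disease progression is met as defined by RECIST 1.1 or death occurs". Subjects who have not progressed are censored at their last disease evaluation.
- **First scan (section 7, footnote 6).** Imaging is due "every odd numbered cycle starting after screening with CT scan before Cycle 3".
- **Objective and numbers.** Section 2.1.2 refers to the "rate in subjects with metastatic uveal melanoma treated with entrectinib and PAC-1". Section 12.3.1 plans "6 subjects from MTD level in Phase 1b and an additional 29 subjects for a projected sample size of 35". Section 12.3 derives 35 as 32 plus 3 for drop-off.

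**The concern.** The only set labelled for efficacy does not fit the primary endpoint. A death before the first scan is a PFS event by definition, yet the subject has had no re-evaluation and so does not meet 12.4.2. Whoever runs the analysis must choose a population, and the heading of 12.4.2 invites the choice that removes the worst outcomes.

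This is a single-arm trial judged against a fixed 38%, so no control group shares the bias. It is also a trial in which treatment activity is reviewed periodically (12.6), so an unassigned population could be chosen after outcomes are known.

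**Working it through.** **Inputs.** Null rate 0.38, alternative 0.65, one-sided 0.05, 90% power, 32 + 3 = 35 subjects (12.3). Cycle length 28 days; first scan before Cycle 3. The number of deaths before that scan is not in the documents, so I assume 0 to 4 of 35. Three is the size of the plan's own drop-off allowance.

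**The plan's own figure.** An exact binomial test with n = 32 succeeds at 18 or more, with type I error 2.7% and power 88.8%. The one-sided normal approximation with continuity correction needs 31. The stated 32 is therefore about right. Ten per cent of 32 is 3.2, and the plan adds 3.

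**Who falls between the definitions.** Two cycles of 28 days put the first scan at about day 56. A subject who dies before then without documented progression is a failure under 2.4.2 and 9.9.3. Under 12.4.2 the same subject is not evaluable. A subject with objective progression before the end of Cycle 1 is kept by the exception.

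**Direction.** With k progression-free among n treated, dropping d early deaths changes k/n to k/(n − d), which is larger whenever k and d are above zero. Kaplan-Meier behaves the same way: removing a subject who died before the scan raises the 3-month estimate. In 9,568 simulated data sets with censoring, removing one early event never lowered it.

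**Size.** Take 18 progression-free among 35, with everyone else followed to 3 months, so that Kaplan-Meier equals the simple proportion. The last column is illustrative, because the plan names no test.

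| Early deaths dropped | Rate | Exact one-sided p against 0.38 |
|---|---|---|
| 0 | 18/35 = 51.4% | 0.0733 |
| 1 | 18/34 = 52.9% | 0.0545 |
| 2 | 18/33 = 54.5% | 0.0393 |
| 3 | 18/32 = 56.3% | 0.0275 |
| 4 | 18/31 = 58.1% | 0.0185 |

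The exact cut-offs are 19/35, 19/34, 18/33, 18/32 and 17/31. Dropping one death therefore changes no decision. Dropping two or three changes it only at exactly 18 progression-free, and dropping four only at 17 or 18. Exactly 18 of 35 has probability 3.7% at a true rate of 0.38 and 3.5% at 0.65.

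**Type I error, illustration only.** Let each of 35 subjects be dropped with probability d, and let f be the share of dropped subjects who are failures. The evaluable success rate is (0.38 − d(1 − f))/(1 − d), and the exact cut-off is applied at each evaluable number.

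- With no exclusions the error is 3.7%.
- With f = 1 it is 4.4% at d = 1/35, 5.5% at 5% and 8.0% at 3/35.
- If exclusion is unrelated to outcome (f = 0.62), it is 3.4% at d = 3/35.
- It passes 5% only when f is about 0.78 or more at d = 3/35, or about 0.93 or more at d = 5%.

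**The case against.** The strongest reply is that the documents already answer the question. The body of 12.4.2 speaks of response, not PFS, and no analysis in 12.5 invokes it. Even ORR does not use it: 12.5.2 divides by subjects with measurable disease, and 9.9.2 refers to all subjects. Sections 2.4.2 and 9.9.3 start the clock at treatment and count death, so a Kaplan-Meier analysis that follows them treats an early death as an event.

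Much of this stands. It means that use of 12.4.2 for PFS is possible but not stated. It does not close the gap. Kaplan-Meier counts deaths only among the subjects it is given, and nothing says who they are. The lack of any analysis that cites 12.4.2 also means its role cannot be read as response only. The heading and the 32 + 3 allowance point to an evaluable subset, while measurement from the start of treatment points to all treated.

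A reader might infer that the plan excludes early deaths from its primary analysis, or that it inflates the type I error to 8%. The documents support neither. The first takes an unassigned set as assigned. The second needs a test the plan does not name, an early-death share it does not give, use of 12.4.2 for PFS, and every dropped subject being a failure.

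**Conclusion.** The point holds as an ambiguity in the primary analysis that should be fixed. No population is assigned to 3-month PFS, and the one set labelled for efficacy conflicts with the endpoint definition over deaths before about week 8.

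The upward direction is certain for those deaths. It is not certain for everyone 12.4.2 leaves out. In a simple proportion, dropping living subjects without a scan could move the rate either way. Under Kaplan-Meier with the 9.9.3 censoring, a living subject never re-scanned is censored at baseline and has no effect.

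The size is about 5 points (56.3% − 51.4% = 4.9) in an example that assumes 3 early deaths among 35, 18 progression-free and full follow-up. With fewer deaths it is smaller, and with none it is zero. The p-values and error rates show scale only and are not properties of the plan.

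**What to change.** - **In 12.5.1:** state that the Phase 2 analysis of 3-month PFS includes every subject who received at least one dose at the Phase 2 dose. This covers the 6 Phase 1b carry-over subjects and any subject later removed and replaced under 5.6.3. Death by 3 months is an event. Living subjects without progression are censored as 9.9.3 already says. The synopsis already names Kaplan-Meier for PFS, so the estimator does not change.
- **In 12.4.2:** state that its set does not define the PFS population, and reconcile it with the ORR denominators in 9.9.2 and 12.5.2, which differ from it and from each other.

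**Cost.** This is a few sentences and needs no change to the planned sample size. The observed rate may be slightly lower if early deaths occur, and the analysed number may slightly exceed 35 if subjects are replaced. Under the illustrative exact rule of at least 19 of 35, power is 93% if 65% is the rate in all treated. If 65% was meant only for subjects who reach the first scan and 3 of 35 die before it, the all-treated rate is 0.65 × 32/35 = 0.594 and power is 79%. The sponsor should say which rate was intended.

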12.5 Data Analysis Plans

12.5.1 Analysis Plans for Primary Endpoint

Phase Ib Analysis of Primary Endpoint

The primary endpoint is determination of the MTD of PAC-1 in combination with entrectinib. The MTD will be defined as the highest explored dose of PAC-1 combined with 600 mg of entrectinib at which ≤ 1 out of 6 subjects have experienced a DLT within the first cycle of therapy. That dose will be recommended for the Phase 2 study (i.e., will be declared the RP2D). At the discretion of the sponsor-investigator, a lower Phase 2 dose may be recommended if other toxicity emerges during the Phase Ib study which does not meet DLT criteria but limits the dose that can be administered cumulatively.

Phase II Analysis of Primary Endpoint

The primary endpoint is determination of the activity of the combination of PAC-1 and entrectinib for treatment of metastatic uveal melanoma, as assessed by 3 months PFS based on RECIST v1.1. Median PFS times will be computed with associated 95% confidence intervals. Kaplan-Meier curves will be plotted.

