STATISTICAL CONSIDERATIONS	
Phase 2 The primary endpoint of the study is 3 month progression-free survival (PFS) rate, using RECIST v1.1, in subjects with metastatic uveal melanoma treated with entrectinib and PAC-1. Kaplan Meier curve will be used to evaluate PFS, and OS; descriptive statistics for response rate, DoR, and toxicity.
 
Sample Size Previous studies in the target population identified PFS at 3 months of 38%.⁶ We hypothesize PFS at 3 months of 65%. Controlling for a probability of Type I error at 0.05 (one-sided), our sample size in Phase 2 is estimated to be 32 to ensure 90% statistical power in successfully detecting an alternative progression free survival rate at 3 months of 0.65, compared to a null rate of 0.38. With 3 additional patients to account for a 10% drop off rate, sample size for phase 2 study will be 35. Sample size analyses were conducted using the PASS software (NCSS, Kaysville, Utah, USA). With Phase 1b study component, the study will need to have 3 subjects from Dose Level 1 of Phase 1b + 6 subjects from Dose Level 2 of Phase 1b (and carried over to Phase 2 study).

TOTAL NUMBER OF SUBJECTS	Total number of subjects for the study is 38
ESTIMATED ENROLLMENT PERIOD	Estimated 18 months
ESTIMATED STUDY DURATION	Estimated 24 months

[figure not shown]
TABLE OF CONTENTS

ABBREVIATIONS	10
1. BACKGROUND AND RATIONALE.....	12
2 STUDY OBJECTIVES AND ENDPOINTS.....	13
3 ELIGIBILITY REQUIREMENTS	15
4 SUBJECT REGISTRATION	18
5 OVERALL DESIGN AND TREATMENT PLAN.....	18
6 DOSE DELAYS/DOSE MODIFICATIONS	24
7 STUDY CALENDAR & EVALUATIONS	28
8. CORRELATIVE STUDIES AND PROCEDURES.....	31
9. CRITERIA FOR DISEASE EVALUATION	33
11. ADVERSE EVENTS.....	39
12 STATISTICAL CONSIDERATIONS.....	45
13 TRIAL MANAGEMENT	49
14 DATA HANDLING AND RECORD KEEPING	51
15 ETHICS.....	52
16 REFERENCES	53
APPENDIX 1: ECOG PERFORMANCE STATUS	55
APPENDIX 2: DRUG INTERACTIONS WITH ENTRECTINIB.....	56

PHASE 1b SCHEMA

The primary objective of the Phase Ib study is to establish the maximum tolerated dose (MTD) of PAC-1 in combination with entrectinib for subjects with metastatic uveal melanoma, by evaluation of toxicity and tolerability.

Phase 1b

[figure not shown]
Dose Level*	PAC-1 Dose (mg, orally)	Entrectinib (mg, orally)	# of Subjects [#]
-1	625 daily	400 daily	3-6
1	625 daily	600 daily	3-6
2	750 daily	600 daily	3-6

*MTD cohort will be initially expanded to 6 patients, and if no DLT, to Phase 2 study.

PHASE 2 SCHEMA

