12. STATISTICAL CONSIDERATIONS

12.1 Study Design

This is a single arm study.

Phase 1b: The primary objective of the Phase Ib dose escalation cohort study is to establish the MTD of PAC-1 in combination with entrectinib in subjects with metastatic uveal melanoma. A standard “3+3” design will be used to establish the MTD. PAC-1 (PO) will be given daily on Days 1 through 21 of each cycle. Entrectinib (PO) will be given daily on Days 1 through 28 of each cycle. Each cycle will equal 28 days. Response will be evaluated after every 2 cycles. Treatment will continue until disease progression based on RECIST criteria or intolerable toxicity.

Phase 2: The primary objective of the Phase II trial is to estimate 3 months PFS using RECIST v1.1 in subjects with metastatic uveal melanoma treated with PAC-1 in combination with entrectinib. PAC-1 (PO) will be given daily on Days 1 through 21 of each cycle. Entrectinib (PO) will be given daily on Days 1 through 28 of each cycle. Each cycle will equal 28 days. Response will be evaluated after every 2 cycles. Treatment will continue until disease progression based on RECIST criteria or intolerable toxicity. Subjects who voluntarily stop the study, have progressive disease, or unacceptable toxicities will be followed for survival every 2 months for 12 months from start of study treatment, then every 3 months for up to 24 months.

Correlative research analyses include examining the relationship between procaspase 3 expression in archived tumor tissue to degree of clinical response.

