12.3 Sample Size and Accrual

Previous studies in the target population identified PFS at 3 months of 38%.⁶ We hypothesize PFS at 3 months of 65%. Controlling for a probability of Type I error at 0.05 (one-sided), our sample size in Phase 2 is estimated to be 32 to ensure 90% statistical power in successfully detecting an alternative PFS rate at 3 months of 0.65, compared to a null rate of 0.38. With 3 additional patients to account for a 10% drop off rate, sample size for phase 2 study will be 35. Sample size analyses were conducted using the PASS software (NCSS, Kaysville, Utah, USA). With phase 1b study component, the study will need to have 3 subjects from Dose Level 1 of Phase 1b + 6 subjects from Dose Level 2 of Phase 1b (and carried over to Phase 2 study). The total number of subjects for the study is 38.

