12.5.2 Analysis Plans for Secondary Endpoints

12.5.2.1 Phase 1b Analysis of Secondary Endpoints

Safety and tolerability by NCI Common Terminology Criteria for Adverse Events (NCI CTCAE) Version 5 on treatment with PAC-1 in combination with entrectinib in subjects with metastatic uveal melanoma.

Proportion of subjects with each grade of adverse events as defined by CTCAE v.5.0 will be computed along with 95% confidence intervals and reported in a tabular and descriptive manner.

PFS at 3 month in subjects with metastatic uveal melanoma treated with PAC-1 in combination with entrectinib.

PFS will be analyzed using the Kaplan-Meier method, and median PFS will be computed with associated 95% confidence interval. Subjects who have not progressed will be right-censored at the date of the last disease evaluation. Kaplan-Meier curves will be plotted. Data will be analyzed using the PROC LIFETEST in SAS.

ORR in subjects with metastatic uveal melanoma treated with PAC-1 in combination with entrectinib.

ORR will be estimated according to RECIST 1.1, by dividing the total number of responders (complete plus partial responses) by number of subjects with measurable disease and the exact 95% confidence interval will be computed.

DoR on treatment with PAC-1 in combination with entrectinib in subjects with metastatic uveal melanoma.

DoR will be evaluated for subjects who achieve CR or PR using the Kaplan-Meier method. For such patients, DoR is defined as the number of months from the start date of CR or PR (whichever response status is observed first) and subsequently confirmed, to the first date that recurrent or progression disease (PD) is objectively documented. If a subject dies, irrespective of cause, without documentation of recurrent or PD beforehand, then the subject's date of death will be used to denote the response end date. Subjects who have not progressed will be right-censored at the date of the last disease evaluation. Median DoR will be computed with associated 95% confidence interval, and Kaplan-Meier curves will be plotted.

OS of subjects with metastatic uveal melanoma treated with PAC-1 in combination with entrectinib.

OS will be analyzed using the Kaplan-Meier method, and median OS times will be computed with associated 95% confidence intervals. Subjects who have not died will be right-censored at the date of the last follow-up, and Kaplan-Meier curves will be plotted. Data will be analyzed using the PROC LIFETEST in SAS.

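### Section 12.5.1 states only median PFS and Kaplan-Meier plots for the Phase 2 primary endpoint; no section gives a confidence interval for the 3-month rate, a test against 0.38 or a success rule, although 12.3 sizes the trial on that comparison

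*Combined protocol and SAP*

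**What the plan says.** **Endpoint.** Section 2.4.2 defines the Phase 2 primary endpoint as a "proportion of alive subjects with metastatic uveal melanoma at 3 months from treatment initiation", without RECIST 1.1 progression. Section 12.1 puts the aim in estimation terms: "The primary objective of the Phase II trial is to estimate 3 months PFS using RECIST v1.1".

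**Sizing.** Section 12.3 and the synopsis set a one-sided type I error of 0.05 and 90% power for an "alternative PFS rate at 3 months of 0.65, compared to a null rate of 0.38". This gives 32 subjects, raised to 35 for a 10% drop-off. Section 12.3.1 reaches the same total with six subjects carried over from Phase 1b and "an additional 29 subjects for a projected sample size of 35".

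**Analysis.** Under its Phase II heading, section 12.5.1 says that activity is assessed by 3-month PFS, and then: "Median PFS times will be computed with associated 95% confidence intervals". Kaplan-Meier plots follow, and nothing else.

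**Elsewhere.**
- The synopsis adds "Kaplan Meier curve will be used to evaluate PFS, and OS".
- Section 9.9.3 adds a censoring rule: "Subjects who have not progressed will be right-censored at the date of the last disease evaluation".
- Section 12.5.2.1, under a Phase 1b entry for PFS at 3 months, again gives only the curve and the median: "PFS will be analyzed using the Kaplan-Meier method, and median PFS will be computed with associated 95% confidence interval".
- Section 12.5.2.2, the Phase 2 secondary analyses, does not cover PFS.
- The benchmark 0.38 appears only in the sample-size text and, as its 38% source figure, in section 1.2.

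**The concern.** In a single-arm trial the efficacy conclusion rests on one comparison with a fixed benchmark. Here the alpha and power belong to a comparison of a rate with 0.38, while the stated primary analysis concerns another quantity, the median. Followed as written, the plan would report a median with its interval and a curve, and would never make the comparison that the trial was sized for.

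The test, the form of the bound and the cut-off would then have to be settled later, possibly with the data in view. The plan does specify an exact 95% interval for ORR, a secondary endpoint, but gives nothing comparable for the primary rate.

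**Working it through.** **Inputs** (sections 12.3 and 12.3.1): p0 = 0.38, p1 = 0.65, one-sided alpha 0.05, power 90%, n = 32 before drop-off and 35 after.

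**1. Reproduce the plan's figure.** The uncorrected normal approximation for one proportion is

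n = [(1.645·√(0.38·0.62) + 1.282·√(0.65·0.35)) / (0.65 − 0.38)]² = [(0.798 + 0.611) / 0.27]² = 27.3, so 28.

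With continuity correction, n = (27.26/4)·[1 + √(1 + 2/(27.26·0.27))]² = 30.9, so 31. The exact binomial test at n = 32 has power 0.888. The stated 32 is thus reproduced to within one subject or about one point of power. The sizing is a one-sample test of the 3-month proportion.

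**2. The decision rule this implies.** Take the smallest r with P(X ≥ r | n, 0.38) ≤ 0.05. Power is P(X ≥ r | n, 0.65).

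| n | Rule | Alpha | Power |
|---|---|---|---|
| 32 | at least 17 | 0.0587 (too large) | 0.942 |
| 32 | at least 18 | 0.0275 | 0.888 |
| 35 | at least 18 | 0.0733 (too large) | 0.966 |
| 35 | at least 19 | 0.0367 | 0.932 |

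No section states either of the valid rules, 18/32 or 19/35.

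**3. Does the choice of method matter?** One-sided 95% lower bounds with no censoring before 3 months, where the Greenwood variance is p(1 − p)/n:

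| Outcome | Linear | Log-log | Exact |
|---|---|---|---|
| 17/32 | 0.386 | 0.378 | 0.373 |
| 18/32 | 0.418 | 0.407 | 0.403 |
| 18/35 | 0.375 | 0.369 | 0.365 |
| 19/35 | 0.404 | 0.396 | 0.392 |

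Against 0.38, all three methods agree at n = 35: 18 fails and 19 passes. At n = 32 they differ only at 17/32, where the linear bound alone passes. That outcome has probability 0.054 if the true rate is 0.65.

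**4. Can the interval for the median replace the test?** No. Its limits locate the time at which PFS equals 0.50. A lower limit above 3 months would indicate a 3-month rate above 0.50, which is a different and stricter statement than above 0.38. A lower limit below 3 months leaves the 0.38 question open. Converting one into the other needs an assumed curve shape, and the plan's own benchmark shows how far that can mislead. Section 1.2 gives PFS of 2.8 months. Read as a median under constant hazard, that implies a 3-month rate of 0.5^(3/2.8) = 0.476, against the 38% quoted in the same section.

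**The case against.** The strongest reply is that the hypothesis is not absent. Section 12.3 and the synopsis state null, alternative, alpha and sidedness, section 12.5.1 says activity is judged by 3-month PFS, and the required curve shows a 3-month estimate. Several objective statements also speak of measuring or estimating the rate. This much stands: it would be wrong to infer that the plan has no hypothesis or cannot yield a 3-month estimate. But a plotted curve is not an interval, a test or a decision rule. Even under a pure estimation aim, 12.5.1 omits the estimate and its precision, and the alpha and power then attach to nothing.

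A second reply is that little room is left for a data-driven choice of method. That also stands, as step 3 shows.

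A reader might infer three stronger things that the documents do not support.
- **That the sample size is wrong.** It reproduces.
- **That power is lost because the two-sided 95% level is used.** Carried over to the rate, that level would move the exact cut-offs to 19/32 (power 80.4%) or 20/35 (power 87.4%). But 12.5.1 attaches it only to the median, and 12.3 says one-sided 0.05.
- **That drop-outs count as failures.** If 10% of 35 did, power at 19/35 would be about 75%. The plan states no such rule and adds three subjects for drop-off.

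It is also fair to say that the exact binomial test is not the only acceptable choice. Kaplan-Meier is the method the plan names for PFS.

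**Conclusion.** The point holds and should be fixed before analysis. The primary analysis in 12.5.1 addresses the median, and no section supplies an interval for the 3-month rate, a comparison with 0.38 or a success rule. Its importance rests on that missing comparison and decision rule alone, not on the choice among methods and not on any loss of power.

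The cut-offs of 18/32 and 19/35 assume a binomial count with every subject's 3-month status known. The agreement of methods at n = 35 assumes no censoring before 3 months.

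Three related gaps are secondary and not part of this conclusion: which analysis set applies (12.4.2 is worded for response), how subjects without a 3-month assessment are counted, and which scan sets 3-month status.

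**What to change.** **In 12.5.1:** make the 3-month PFS rate the primary analysis, tested against 0.38 at one-sided 0.05. Report the matching one-sided 95% lower bound, which is the lower limit of the two-sided 90% interval. Make median PFS supportive. The exact binomial test fits the proportion in 2.4.2 and the sizing in 12.3, with success at 18/32 or more, or 19/35 or more, and the exact cut-off for any other denominator fixed by the same rule. A Kaplan-Meier 3-month estimate with a pre-stated one-sided 95% bound is equally acceptable if its interval method is named.

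**In 12.3:** name the test. If it is the exact binomial, give power as about 89% at 32 evaluable subjects.

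**Cost:** wording in two sections, with no more patients. Settling the secondary gaps costs more. It would also touch 2.4.2, 9.9.3, 12.4.2 and the synopsis, and choosing the scan is more than wording. Footnote 6 of the study calendar places scans before Cycles 3 and 5, which with 28-day cycles is after about 2 × 4 = 8 and 4 × 4 = 16 weeks. Neither falls at 3 months, so the choice bears on what the rate means beside the 38% benchmark.
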